7.4.1.3 Site and Sample Time Balance

Each groin and abdomen sample site is divided into four areas and two of these areas are sampled once – one at baseline and one at 10 minutes ± 30 seconds, and two areas will not be used. Therefore, for any groin or abdomen site there are 24 possible sampling orders.

The number of subjects required for a completely balanced block design for all factors at once (study products, left/right, and sampling order) is a multiple of 144 (3*2*24). The exact subject numbers may make it infeasible to provide a completely balanced block design, so the following priority order will be used for design:

1. Treatment combinations will always be applied in balanced blocks, with the block size being sufficient to preserve the ratio of 1:1:1 for all three study products.
2. Left/right balance will be preserved – each treatment will be applied an equal number of times to each side of the body.
3. Sampling orders will be assigned in blocks of 24 as much as possible. If the final number of subjects is not a multiple of 24 the remaining subjects will be assigned random non-duplicative sample orders from the 24 possible sample orders.
4. The blocking will be adjusted based on the final subject numbers to be as balanced as possible with respect to all three factors above at once, with priority using the order listed above.

The Investigator is responsible for ensuring that the randomization is followed. A basic outline of a randomization schedule for the abdominal and groin sites is provided in Appendix 22.4. The final randomization schedule will be prepared by the study statistician before the initial treatment.

Subjects will be identified by their initials, and a subject number.

- Randomized subjects will be assigned numbers ranging from 001 to a three digit number equal to the total number of test subjects needed (36 for the estimated numbers).

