3.3 Study Design

This single site study is a randomized, blinded design employing a minimum of 36 healthy volunteers, where each subject receives two of the planned treatments on the abdomen and groin.

Treatment materials for the following treatment groups will be blinded with treatment codes A or B:

- Thermally treated cloth impregnated with 0.4% w/v octenidine dihydrochloride aqueous solution (IP: Investigational Product).

- Thermally treated cloth impregnated with vehicle formulation (VC: Vehicle Control).

The 0.9% Saline Control (SC) cannot be blinded due to product application requirements and will be assigned to treatment code C.

Out of the minimum 36 evaluable subjects, 12 subjects will receive treatments from both A and B, 12 subjects will receive treatments from both A and C, and 12 subjects will receive treatments from both B and C to achieve 24 test sites from A, B and C for groin and abdominal regions. The application will be randomized so that each treatment is applied on an equal number of left and right sides of the body. Due to baseline requirements the final data set may be imbalanced with regard to right and left sides upon achieving the minimum number of qualifying body sites.

Subjects will be sampled for treatment day baseline microbial populations on randomly assigned sites of the abdominal and inguinal areas on both sides. Subjects will have samples collected at baseline and 10 minutes (± 30 seconds) on both abdomen and inguinal sites. All sampling times will be calculated from the completion of the dry time of each product following application.

There is a neutralization test before the main treatment study. Note: this statistical analysis plan is only for the Main Treatment study and does not include the analysis for the Neutralization study. The analysis for the Neutralization study will be conducted by the clinical site and included in the final clinical report.

The group treatments and number of treatment sites planned for each group for the main treatment study are shown in Table 1.

Table 1: Group treatments and number of treatment sites planned

Arm	Treatment	Number of evaluable treatment sites per anatomical site
Investigational Product (IP)	Thermally treated polyester cloth impregnated with 0.4% w/v octenidine dihydrochloride	24
Vehicle Control (VC)	Thermally treated polyester cloth impregnated with vehicle formulation	24
Saline Control (SC)	0.9% normal saline applied with polyester cloth	24

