3.5 Acceptance Criteria

The following table summarizes the minimum baseline criteria for each of the test sites and the expected minimum efficacy standards (superiority criteria).

Table 2: Minimum Treatment Baseline and Expected Mean Log₁₀ Reduction per Anatomical Site

Anatomical Site	Treatment Day Baseline Criteria	Expected Efficacy Standards
Abdomen	3.00 to 5.50 log ₁₀ CFU/cm ²	At 10 minutes, the lower two-sided 95% confidence bound of the average treatment effect of IP vs. VC and IP vs. SC should be greater than 1.2 log ₁₀
Groin	5.00 to 7.50 log ₁₀ CFU/cm ²	At 10 minutes, the lower two-sided 95% confidence bound of the average treatment effect of IP vs. VC and IP vs. SC should be greater than 1.2 log ₁₀

4 Sample Size

This is a phase 2 study to assess the immediate antimicrobial effect of the Investigational Products relative to the two negative controls using a log reduction study according to the procedures outlined in the Food and Drug Administration Tentative Final Monograph (TFM) for *Effectiveness Testing of a Patient Preoperative Skin Preparation* (FR 59:116, 17 June 94, pp. 31450-31452) and the test criteria outlined in the deferral letters from the FDA published on January 19, 2017. The purpose is to inform design of future efficacy studies. Therefore, no sample size calculation was performed to provide statistically-powered evidence of efficacy as part of this study. The sample size is deemed adequate for these purposes.

5 Intended Statistical Software

R 3.2.0 (2015-04-16) or later version if updated.

6 Data

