7.4 Analysis Methods

For each body site, when per-protocol data are different from mITT data for \log_{10} CFU/cm², log reduction, or product expression volumes, per-protocol analysis and mITT analysis will be performed separately using the same statistical methods. The following analysis methods will be applied to both per-protocol analysis and mITT analysis, both abdomen and groin.

An alpha level of 5% (two-sided) is used for all analyses.

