7.4.1 Primary Analysis

An analysis of variance (ANOVA) of the baseline \log_{10} CFU/cm² values will be performed separately for abdomen and groin. In each model, there will be a random subject effect, a fixed treatment effect, a fixed body side effect and the interaction between treatment and body side. Pairwise comparisons with Tukey's method will be made for \log_{10} CFU/cm² to determine if there is any significant difference between treatments at baseline after adjusting body side (e.g., randomization has produced treatment arms with similar baseline CFU values) for each body site.

The primary purpose of the study is to compare the immediate antimicrobial activity of the Investigational Products to the Negative Control according to the methods described in the FDA TFM with the statistical analyses outlined in a deferral letter published January 19, 2017 for superiority.

Evaluate the treatment effect at 10 minutes for Investigational Product (IP) vs. Vehicle Control (VC) / Saline Control (SC) for abdomen and groin by comparing to a superiority margin of 1.2 \log_{10} .

- Ho: treatment effect of IP vs. VC/SC correcting for pre-treatment \log_{10} bacterial counts $\leq 1.2 \log_{10}$
- Ha: treatment effect of IP vs. VC/SC correcting for pre-treatment \log_{10} bacterial counts $> 1.2 \log_{10}$

Ho is the null hypothesis and Ha is the alternative hypothesis.

A linear regression model for each body site will be used for primary analyses. In the model, the response is the post-treatment \log_{10} bacterial counts and predictors are the treatment effect as a fixed effect and the pre-treatment \log_{10} bacterial counts as a covariate. The two-way interaction between the treatment and pre-treatment \log_{10} bacterial counts will also be explored. If there is no significant interaction detected, the interaction term will be removed from the model and the average difference between treatments correcting for pre-treatment bacterial loads will be estimated from the linear regression model. If there is a significant interaction detected between treatment and pre-treatment \log_{10} bacterial counts, the average difference between treatments will be estimated from the linear regression model at the average of the covariate.

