The average treatment effect along with 95% confidence interval between IP and VC/SC will be estimated from the model above for each body site and compared to a superiority margin of 1.2. If the two-sided 95% lower confidence bound $> 1.2 \log_{10}$, the null hypothesis for superiority is rejected and it is concluded that IP is superior to VC/SC by passing the superiority margin of $1.2 \log_{10}$. Otherwise the superiority criteria cannot be passed.

The primary analysis will be based on the modified Intent to Treat (mITT) data set and the supportive analysis may be conducted using the per-protocol data set, as described in Section 6.

Since the study will declare success when and only when superiority is demonstrated for both IP vs. VC and IP vs. SC for both abdomen and groin, no multiplicity adjustment for multiple primary objectives is required^[1].

An example for results of comparisons above can be found in Table 8. All results that do not meet the targets are highlighted.

Table 8: Example: results for for IP vs. VC and SC for Groin

Comparison	N Pairs	Average Treatment Effect	Conf Int	Meet Superiority Criteria
IP vs. VC	24	1.23	0.90, 1.50	No
IP vs. SC	24	1.65	1.31, 1.99	Yes

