7.4.3.2 Product Expression Volumes/Weight

An analysis of variance (ANOVA) of the applied volumes/weight will be performed separately for each body site based on mITT data and/or per-protocol data. In the model, there will be a random subject effect, a fixed body side (left or right) effect, a fixed treatment effect and the interaction between fixed effects. ANOVA table will be checked to see whether the treatment has a significant effect on product expression volumes as well as the interaction. If a significant difference is found, subgroup comparisons with Tukey's method will be made to determine which pair of comparisons shows significant difference.

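### The primary regression omits body side, a factor the randomisation balances and two other SAP models adjust for; adding it is a minor, nearly free safeguard against a realised left/right imbalance.

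*SAP*

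**What the plan says.** - **Primary model.** SAP 7.4.1 fits one regression per anatomical site to the 10-minute log10 count. Its "predictors are the treatment effect as a fixed effect and the pre-treatment" log10 count, and the treatment-by-baseline interaction is dropped if not significant. The protocol summary and protocol 17.3.1 give the same terms.
- **Decision rule.** The lower limit of the two-sided 95% interval is "compared to a superiority margin of 1.2" log10, for the investigational product (IP) against the vehicle control (VC) and the saline control (SC), on abdomen and groin. All four comparisons must pass.
- **Side in the design.** Each subject receives one treatment on the left and another on the right. The second blocking priority in protocol 7.4.1.3 is that "each treatment will be applied an equal number of times to each side of the body".
- **Side in the final data.** SAP 3.3 says that because of the baseline requirements "the final data set may be imbalanced with regard to right and left sides". Protocol 7.4.1.2 says the same.
- **Side in the other models.** The baseline ANOVA, also in SAP 7.4.1, has "a fixed body side effect and the interaction between treatment and body side". The product-weight ANOVA in SAP 7.4.3.2 has "a fixed body side (left or right) effect". The log-reduction ANOVA in SAP 7.4.3.1 has treatment as its only predictor.

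Neither document explains why the two efficacy models leave side out.

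**The concern.** Left and right are built into the treatment comparison. Within a subject, every IP-versus-control contrast is also a left-versus-right contrast. A side difference cancels only if each treatment keeps about the same share of left sites after the baseline exclusions. The design secures this by blocking. The primary analysis has nothing to fall back on if exclusions upset the balance, a possibility both documents mention.

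Two effects are possible. If the analysed sites are unbalanced by side, part of any side difference enters the estimate that is compared with 1.2 log10. If they are balanced, the side difference stays in the residual and widens the interval. A random subject effect, which the primary model also lacks, would not remove a left/right difference, so this is a separate point.

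**Working it through.** **Design figure.** 36 subjects × 2 treatments ÷ 3 treatments = 24 sites per treatment per anatomical site, as SAP 3.3 states. Full balance is 12 left and 12 right per treatment.

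**Inputs**
- Margin 1.2 log10 (SAP 7.4.1); alpha: "An alpha level of 5% (two-sided) is used for all analyses" (SAP 7.4).
- Side difference *d* remaining after baseline adjustment: not in the documents; assumed 0.1 to 0.5 log10.
- Residual SD: not in the documents; assumed 1.0 to 1.1. The SAP's Table 6, an example only, shows 10-minute SDs of 0.72 to 1.10.

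**Shift from a realised imbalance.** Shift = *d* × (left share in IP − left share in control).

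| IP left/right v control left/right | Difference in left share | *d* = 0.1 | *d* = 0.2 | *d* = 0.5 |
|---|---|---|---|---|
| 12/12 v 12/12 | 0 | 0 | 0 | 0 |
| 14/10 v 10/14 | 4/24 | 0.017 | 0.033 | 0.083 |
| 16/8 v 8/16 | 8/24 | 0.033 | 0.067 | 0.167 |

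**How likely are such imbalances?** Assume each arm starts balanced by side, and 24 sites qualify at random, independently between arms, out of 36, 48 or 72. The left count in each arm is then hypergeometric.
- A gap of at least 4 left sites between the arms, in either direction: about 8%, 15% and 22%.
- A gap of at least 8: about 0.01%, 0.2% and 0.8%.

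So the 14/10 v 10/14 row is plausible, and the 16/8 v 8/16 row is very unlikely.

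**Interval width when sides are balanced.** The omitted side difference adds *d*²/4 to the residual variance, and width grows by √(1 + (*d*²/4)/SD²).
- *d* = 0.2, SD 1.0: 0.01 added; √1.01 = 1.005, or 0.5% wider.
- *d* = 0.5, SD 1.0: 0.0625 added; √1.0625 = 1.031, or 3.1% wider.
- *d* = 0.5, SD 1.1: √(1 + 0.0625/1.21) = 1.026, or 2.6% wider.

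The percentage rises if the SD is smaller: at 0.72, √(1 + 0.0625/0.518) = 1.059.

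**Simulation of the primary model with and without side.** True effect set at 1.2; SD 1.1; side difference 0, 0.2 or 0.5; within-subject correlation 0 or 0.5; either all sites of 36 subjects qualifying, or a random 67% of the sites of 54 subjects; 4,000 runs per scenario.
- Average error of the estimate: within about 0.012 log10 of zero in every scenario, with or without side.
- One-sided false-positive rate at the margin (nominal 0.025): 0.009 to 0.026 without side, 0.010 to 0.027 with it.
- Mean interval half-width at *d* = 0.5: about 0.65 without side, 0.64 with it.

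**Cost of the extra term.** With 72 sites the current model leaves 72 − 4 = 68 degrees of freedom; adding side leaves 67. The t critical value moves from 1.9955 to 1.9960.

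**The case against.** The case for leaving the model alone has several sound parts.

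- **No systematic bias.** Inclusion in the mITT set depends on the Treatment Day baseline count, sampled before product is applied, and treatment is randomised to side. A realised imbalance is therefore chance, of either sign. This stands, and the simulation agrees.
- **Baseline already adjusts.** The covariate comes from the same test area as the post-treatment sample, so it absorbs at least part of a left/right difference in resident flora. This stands; *d* must be read as what remains afterwards.
- **No evidence of a side effect.** None is reported in the documents. This stands; the range is an assumption.
- **Low stakes.** SAP section 4 says "no sample size calculation was performed to provide statistically-powered evidence of efficacy as part of this study", and all four comparisons must pass, so a favourable shift in one cannot by itself produce success. This stands, although an unfavourable shift in one could prevent it.
- **Change is not confined to the SAP.** The protocol gives the same predictors, and both documents tie the analysis to FDA letters that are not reproduced in them. Whether those letters prescribe the model cannot be told from the documents. This is a reason to check, and to amend both texts together.

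None of this shows that omitting side is preferable. It shows that the gain is small.

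**Conclusion.** The point holds as a minor, unexplained inconsistency with a nearly free remedy. The primary model omits a factor that the randomisation balances and that two of the SAP's three other linear models carry. For an assumed remaining side difference of 0.1 to 0.5 log10, a plausible imbalance of 14/10 v 10/14 would shift an estimate by 0.017 to 0.083 log10. With balanced sides the interval is at most about 2 to 3% too wide, at a residual SD of 1.0 to 1.1. These sizes rest on assumed values of the side difference and the SD.

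Three stronger readings are tempting, and the documents do not support them:
- **That all the other models include side.** The log-reduction ANOVA does not.
- **That the SAP expects imbalance.** Both documents say only that it may occur.
- **That the omission biases the trial towards success.** Exclusions rest on pre-treatment counts, the average error is essentially zero, and false positives are not inflated. The loss of precision works against a claim of superiority.

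**What to change.** In SAP 7.4.1, add body side (left or right) as a fixed main effect, without interaction, to the primary regression for each anatomical site, and report the IP versus VC and IP versus SC differences from that model. Make the same addition to the log-reduction ANOVA in SAP 7.4.3.1. Align the model wording in the protocol summary and protocol 17.3.1, so that the two documents still specify the same primary model. Before doing so, the sponsor should confirm that the FDA letters the plan cites do not prescribe a model without side; if they do, state that as the reason for the omission.

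The cost is a short wording change in both documents and one degree of freedom. No new data are needed, since side is set by the randomisation schedule and already used in two SAP models. Specifying the term in advance also avoids a choice between adjusted and unadjusted results after an imbalance has been seen.

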7.4.2 Secondary Analysis

The ITT data set (all randomized subjects) will be considered evaluable for safety. Skin irritation scores will be reported for any subject who is scored with a 1 or more at any observation (baseline treatment day or the 10 minute post-application time point) in any category for any site.

Based on the protocol, subjects who receive an irritation score of 1 or greater (any redness, swelling, rash, or dryness present at any treatment area) for any individual skin condition prior to the treatment Day baseline sample collection will be excluded from the study and will not be randomized.

Adverse Events (including post treatment skin irritation scores of 3), will also be summarized. Summary tables will present incidence rates of adverse events by treatment group for all subjects who enter the treatment period. Listings of Adverse Events will be provided.

The statistical significance of differences in skin irritation between the Investigational Product, Vehicle Control and Saline Control will be evaluated using Fisher's exact test on skin irritation data summarized as follows: any reaction above zero (no reaction) on the skin irritation rating scale for any category (erythema, edema, rash, and dryness) will be considered a positive signal for that substance. If Fisher's exact test shows there is an overall significant treatment effect, Fisher's exact test or two-proportion test with Score method with multiplicity adjustment on the alpha level may be used for multiple sub-group comparisons to find out which comparisons show the difference. Odds ratio (odds of having positive signals for one treatment / odds of having positive signals for the other treatment) using Fisher's exact test or the difference in percentage of positive signals between treatments using a two-proportion test may be calculated along with the confidence interval for each category at the certain time interval.

Examples for Fisher's exact test and two-proportion test with Score method are shown below.

```
> # overall treatment effect
> irr_tab <- matrix(c(2, 1, 3, 22, 23, 21),
+   nrow = 3,
+   dimnames =
+   list(c("A", "B", "C"),
+        c("Positive (Score > 0)", "Non-positive (Score = 0)")))
> irr_tab
```

	Positive (Score > 0)	Non-positive (Score = 0)
A	2	22
B	1	23
C	3	21

```
> irr <- fisher.test(irr_tab, alternative = "two.sided",
+   conf.level = 0.95)
> print(irr)
```

Fisher's Exact Test for Count Data

```
data: irr_tab
p-value = 0.8654
alternative hypothesis: two.sided
```

```
> # subgroup comparisons
> library(PropCIs)
> print(diffscoreci(2, 22, 1, 23, conf.level = 0.984))
```

```
data:
98.4 percent confidence interval:
-0.1934747 0.3014313
```

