7.4.1.1 Treatment Balance

Each subject will receive two of the three possible treatments, one on the right side of the body and one on the left. A minimum of 36 evaluable subjects will be required to achieve a total of at least 24 test sites for groin and abdominal regions for each treatment.

The treatment assignments will be balanced such that the number of readings per anatomical site matches the calculated requirements.

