13.0 SAFETY

13.1 Adverse Event Definitions

Adverse Event (AE): Any unfavorable and unintended sign (including an abnormal laboratory finding), symptom or disease in a subject that is temporally associated with the use of an investigational product or procedures, even if the event is not considered to be related to the study product or procedures.

This includes events not seen at initial assessment (Pre-Treatment Day) and events that have worsened if present at initial assessment. The term AE will refer to all adverse events (serious and non-serious) occurring during participation in a study of either investigational devices and/or drugs.

Serious Adverse Event (SAE): An SAE is any AE occurring during study participation that results in any of the following outcomes:

- Death

- Life Threatening (refers to any event in which the subject was at risk of death at the time of the event; it does not refer to an event which hypothetically might have caused death if it were more severe)
- Hospitalization or prolongation of a hospital stay
- Persistent or significant disability or incapacitation (refers to any event which results in a substantial and/or permanent disruption of the subject's ability to carry out normal life functions)
- Required intervention to prevent permanent impairment/damage
- Congenital anomaly/birth defect
- Important medical event that may require intervention to prevent one of the preceding conditions.

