17.3.2 Secondary Analysis

The ITT data set (all randomized subjects) will be considered evaluable for safety. Skin irritation scores will be reported for any subject who is scored with a 1 or more at any observation (baseline treatment day or the 10 minute post-application timepoint) in any category for any site.

Adverse Events (including post treatment skin irritation scores of 3), will also be summarized. Summary tables will present incidence rates of adverse events by treatment group for all subjects who enter the treatment period. Listings of Adverse Events will be provided.

The statistical significance of differences in skin irritation between the Investigational Products and Negative Controls will be evaluated using Fisher's exact test on skin irritation data summarized as follows: any reaction above zero (no reaction) on the skin irritation rating scale for any category (erythema, edema, rash, and dryness) will be considered a positive signal for that substance. If Fisher's exact test shows statistically significant skin irritation between the three study products, a secondary analysis will be conducted to determine how the reactions differ.

17.3.3 Exploratory Analysis:

Log Reductions:

The following descriptive statistics for \log_{10} CFU/cm² reductions will be computed for the mITT and Per Protocol populations for each product tested, grouped by anatomical site at the 10 minute application sampling time point: mean, median, standard deviation, minimum, maximum, and count.

Antimicrobial activity will be compared using \log_{10} reductions between the Investigational Product, and both negative controls for each body area at the 10-minute sampling time. Differences in \log_{10} CFU/cm² reductions between treatments and confidence intervals will be estimated by an analysis of variance (ANOVA). In the ANOVA model, the response is the \log_{10} reduction and the predictors are treatment and time point as well as the interaction between treatment and time point. The average difference in log reduction between treatments per time point will be estimated. However, all conclusions for the treatment effect (difference between treatments in \log_{10} reduction) will be based on the primary analysis only.

17.3.4 Informational Analysis:

Product Expression Volumes:

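### Skin irritation is compared with an unpaired Fisher test on 72 entries from 36 subjects, and the rule for attributing non-local adverse events is not stated

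*SAP*

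**What the plan says.** Protocol 7.4.1.1 sets the design: "Each subject will receive two of the three possible treatments, one on the right side of the body and one on the left". SAP 3.3 gives the allocation: "12 subjects will receive treatments from both A and B, 12 subjects will receive treatments from both A and C", and the remaining 12 receive B and C. Three product groups of 24 are therefore built from 36 people, and every person is in two of them.

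For irritation, SAP 7.4.2 specifies Fisher's "exact test on skin irritation data summarized as follows": a product scores positive if any of the four categories (erythema, edema, rash, dryness) is rated above zero. The worked example is a 3×2 table with 24 per row. Pairwise comparisons follow only if the overall test is significant. SAP 7.4 adds: "An alpha level of 5% (two-sided) is used for all analyses". No subject term or pairing appears in this analysis. The SAP does use a random subject effect for the baseline counts (7.4.1) and for the applied product weight (7.4.3.2).

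For adverse events, SAP 7.4.2 states: "Summary tables will present incidence rates of adverse events by treatment group for all subjects who enter the treatment period". Protocol 17.3.2 likewise promises "incidence rates of adverse events by treatment group for all subjects who enter the treatment period". Both add listings. Protocol 13.1 defines an adverse event broadly: "Any unfavorable and unintended sign (including an abnormal laboratory finding), symptom or disease in a subject". No significance test on adverse events is planned.

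**The concern.** Fisher's test takes its p-value from a distribution in which all 72 entries are exchangeable between rows. Here they are not, because two entries from one person always sit in two different rows. If some people have reactive skin, the two entries move together and the test's error rate is not the nominal one. Safety is the only secondary objective, and the overall test controls whether any pairwise comparison is made. An overall test that is too strict can therefore stop a real irritation difference from being examined.

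The adverse event table raises a simpler question. Irritation is rated within the treated site, so it belongs to one product. An event that cannot be placed on one side, such as a generalised reaction, has no defined column for someone who received two products.

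**Working it through.** **Inputs.** From the documents: 36 subjects in pairs 12/12/12, 24 entries per product, two-sided alpha 5%. Not in the documents, and therefore assumed: reaction rate 10% to 30%, and a range of within-subject correlations.

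**1. The plan's own figure.** Enumerating all 3×2 tables with the margins of the SAP example (2/24, 1/24, 3/24) gives p = 0.8654, as printed. The test is thus the ordinary unpaired one. A separate slip: the example pairwise interval enters 22 and 23, the non-positive counts, as denominators. With 24 and 24 the 98.4% interval is -0.190 to 0.280, against the printed -0.193 to 0.301.

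**2. Direction of the error.** Let p be the common reaction rate and ρ the correlation between a subject's two yes/no outcomes. Each product proportion has variance p(1-p)/24. Any two products share 12 subjects, so their covariance is 12ρp(1-p)/24² = ρp(1-p)/48. Hence

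Var(difference) = 2p(1-p)/24 - 2ρp(1-p)/48 = [2p(1-p)/24] × (1 - ρ/2).

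Fisher's test in effect uses the first factor only. The true variance is 0.85, 0.75 and 0.60 of that at ρ = 0.3, 0.5 and 0.8, so the test is too strict.

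**3. Type I error at nominal 5%, one entry per subject and product** (20,000 simulated trials per cell, beta-binomial outcomes):

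| Rate | ρ = 0 | 0.3 | 0.5 | 0.8 |
|---|---|---|---|---|
| 10% | 2.9% | 1.5% | 0.7% | 0.2% |
| 20% | 3.9% | 2.3% | 1.4% | 0.4% |
| 30% | 4.4% | 2.3% | 1.5% | 0.4% |

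If correlation is instead placed on a latent normal reactivity score cut at a threshold, the values at a 20% rate are about 4.0%, 2.2% and 1.2% at latent correlation 0, 0.5 and 0.8. The shortfall at zero correlation is Fisher's usual discreteness. The rest is due to clustering.

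**4. One illustrative table.** Take reactions in 9, 3 and 3 of 24 (test product, vehicle, saline). Fisher gives p = 0.073 whatever the pairing. Re-randomising pairs and sides to whole subjects gives p of about 0.01 to 0.02 if all six control reactions are in subjects who also reacted to the test product, about 0.03 if four are, 0.05 to 0.07 if two are, and 0.07 to 0.10 if none are. The ranges reflect the choice of statistic and where the remaining reactions fall. The answer depends on information that Fisher's test discards.

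**5. If sites were pooled.** With abdomen and groin entered separately (48 per product), two entries from one subject also share a row. In a latent model with rates of 10% to 30%, type I error was 9.0% to 9.7% with subject and side variance shares of 0.3 and 0.4, and 11.0% to 12.6% with shares of 0 and 0.7. When all four sites correlated equally or not at all, it was 4.3% to 5.0%.

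**6. The alternative.** A re-randomisation test that keeps each subject's outcomes together had type I error of 2.7% and 4.3% at latent correlation 0 and 0.8 (rate 20%). Its power for assumed rates of 40%, 10% and 10% was 70% and 78%, against 71% and 71% for Fisher. These come from 600 trials each, so they carry a Monte Carlo error of about 2 points.

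**7. Adverse event attribution.** Suppose only the test product causes a non-local event, at rate q, and each event is counted under every product received. The test product column shows 24q/24 = q. Half of each control group also received the test product, so each control column shows 12q/24 = q/2. At q = 25% the table reads 25%, 12.5%, 12.5%.

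**The case against.** The study is phase 2, makes no powered claim, and attaches no pass/fail threshold to safety. A conservative screening test leads to no wrong approval, the power difference is small, and the correlation that drives it is assumed. All of that stands, and it limits the size of the point. It does not make the reference distribution right, and the SAP already recognises the subject effect in two other analyses.

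On pooling, SAP 7.4 says its methods apply to both abdomen and groin, and the example has 24 per row. Both lean away from 48 per product. But 7.4.2 defines a positive signal for the product rather than for a site, and never states the unit. Pooling is therefore a possibility to close off and not a planned analysis.

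On adverse events, Protocol 13.3 has the suspected product recorded for each event, so a table by suspected product is an available reading, and the listings keep each event traceable. That stands as well. No sentence says the table uses that field, and SAP Table 3 counts subjects under each treatment received, so the rule remains open.

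**Conclusion.** The irritation test is wrong for this design as written. In the layout the SAP illustrates it is conservative if reactions cluster within subjects: about 2.2% and 1.2% instead of 5% at a 20% rate and latent correlations of 0.5 and 0.8. The rate and correlation are assumptions. The practical loss is a few points of power. Under pooling the error could go the other way.

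Two stronger readings are tempting and not supported. A reader might infer that the plan charges systemic test-product events to the controls and halves the difference. That follows only if events are counted under every product received, which no passage states. A descriptive incidence table also does not by itself assume independent people, and since no adverse event test is planned, no p-value belongs to this part. A reader might also infer from the 9/3/3 table that Fisher's test routinely hides a real signal. The conclusion at 5% changes there only when most control reactors also reacted to the test product.

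**What to change.** In SAP 7.4.2 and Protocol 17.3.2:

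- Define the unit of the irritation test: either abdomen and groin separately, or one result per subject and product.
- Keep the Fisher statistic, but obtain the overall and follow-up p-values by re-randomising product pairs and sides to whole subjects as in the actual schedule. Retain the multiplicity adjustment already foreseen for the follow-up comparisons.
- State the attribution rule for adverse events. Tabulate application-site events by the product applied there. Tabulate all other events by randomised pair, with totals for subjects exposed and not exposed to the test product.

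The cost is SAP and protocol wording and one short program, with no new data. The downside is about 1 to 2 points of power if a subject's two reactions are in fact independent.
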